13 METHODS OF EFFICACY ANALYSES

13.1 Analysis of Efficacy Endpoints

Descriptive statistics for all exploratory efficacy endpoints listed in Section 12.1 will be tabulated by treatment group at scheduled timepoints. The summaries of the change from Baseline results will be presented by treatment group at scheduled timepoints. For change from Baseline values at each post-Baseline visit, LS means and standard errors (SE), the between-group difference in LS means with the corresponding 95% CI, p-value, and effect size will also be presented.

13.2 Mixed Model Repeated Measures (MMRM)

The MMRM method will be used for selected continuous exploratory endpoints, in which missing data is assumed to be missing at random. The dependent variable will be the change from Baseline. The independent variables in the model will include the fixed categorical effects of treatment group, region, visit, and treatment-by-visit interaction, as well as the continuous, fixed covariates of Baseline score and Baseline score-by-visit-interaction. An unstructured covariance matrix will be used to model the within patient errors, and the Kenward-Roger approximation will be used to adjust the denominator degrees of freedom. Observed cases will be analyzed in the model and least squares (LS) means will be estimated using observed margins.

In the event that the model fails to converge using the unstructured covariance matrix, then the following covariance structures will be modeled in the following order:

1) Heterogeneous Toeplitz

- 2) Heterogeneous compound symmetry
- 3) Heterogeneous autoregressive(1)
- 4) Toeplitz
- 5) Compound symmetry
- 6) Autoregressive(1)
- 7) Variance components

The first covariance structure that allows for convergence will be selected for the final model. For change from Baseline values at each post-Baseline visit, LS means, standard errors (SEs), and the between-group difference in LS means with the corresponding two-sided 95% confidence intervals (CIs), p-values, and effect sizes will also be presented. LS means ±SE over time for the change from Baseline values by treatment group will be presented in line plots.

At each visit, the effect size (Cohen's d) for the change from Baseline between the treatment groups will be calculated using the following formula:

$$Effect \ size = \frac{LS \ mean \ difference}{\sqrt{variance}}$$

The variance at a given visit will be obtained from the covariance matrix estimated for the MMRM model. The sign (+ or -) of the effect size will be chosen so that a positive value favors pimavanserin.

13.3 Analysis of Covariance (ANCOVA)

For those endpoints that are analyzed using ANCOVA (i.e., EQ-5D-5L VAS), the dependent variable will be the change from Baseline, and the independent variables in the model will include treatment group and region as factors, and Baseline score as a continuous covariate. LS means will be estimated using observed margins; the LSM, SE, LSM treatment difference, 95% CI of treatment difference, and p-value for treatment differences from the ANCOVA model will be reported. Observed cases excluding missing values, and the last observation carried forward (LOCF) method of imputation for missing data will be used. If necessary, the Baseline value will be carried forward.

13.4 Exploratory Efficacy Analyses

13.4.1 CGI-S

Observed CGI-S scores will be summarized using descriptive statistics at Baseline, Weeks 1, 2, 4, 6, and 8/ET. The change from Baseline values will be summarized descriptively at Weeks 1, 2, 4, 6, and Week 8/ET. The change from Baseline in CGI-S score will also be

analyzed using the MMRM model as described in Section 13.2, except that anti-dementia medication use at Baseline will be included in the model as a factor.

13.4.2 CGI-I

13.4.2.1 MMRM

Observed CGI-I scores will be summarized using descriptive statistics at Weeks 1, 2, 4, 6, and 8/ET. The CGI-I scores will also be analyzed using the MMRM model as described in Section 13.2, with the following modifications:

- the dependent variable is the observed score
- Baseline CGI-S score is used as the covariate
- Anti-dementia medication use at Baseline will be included in the model as a factor

13.4.2.2 Responder Analysis

A responder analysis will be conducted in which a CGI-I score of 1 (very much improved) or 2 (much improved) will be counted as a responder. At each post-Baseline timepoint the proportion of responders will be summarized by treatment group.

Two types of responder analyses will be performed:

- Observed case responder analysis, in which subjects with missing values at a given visit are excluded from the analysis for that visit, will be performed
- Missing values imputed as non-responders for the given visit

The adjusted difference in percent responders between treatment groups (pimavanserin group minus placebo group) using the Cochran-Mantel-Haenszel weighting scheme stratified by region (North America, Europe, or rest of world), p-value, and Newcombe's 95% CI will be presented.

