1.3.2 Alzheimer's Disease Psychosis

Evidence from the recently completed Phase 2 study (ACP-103-019) suggests that pimavanserin is effective in reducing hallucinations and delusions in patients with psychosis in Alzheimer's disease (Ballard et al. 2018).

Study ACP-103-019 was a Phase 2, 12-week, randomized, double-blind, placebo-controlled, single-center study to assess the safety and efficacy of pimavanserin 34 mg once daily in nursing home subjects with ADP. Eligible subjects were required to have a score of 4 or greater on either the hallucinations or delusions scale of the Neuropsychiatric Inventory-Nursing Home Version (NPI-NH) or a total combined Hallucinations and Delusions score of 6 or greater. The primary efficacy endpoint was change from Baseline to Day 43 in the NPI-NH psychosis score (Delusions+Hallucinations domains).

A total of 181 subjects were randomized (n=90 pimavanserin and n=91 placebo) with 178 subjects included in the Full Analysis Set (FAS; n=87 pimavanserin and n=91 placebo). The mean (standard error [SE]) age of subjects was 85.9 (0.48) years. The mean (SE) Baseline NPI-NH psychosis score for all FAS subjects was 9.8 (0.39) with comparable mean scores in the pimavanserin (9.5) and placebo (10.0) groups. The mean (SE) Mini-Mental State Examination (MMSE) score for all FAS subjects was 10.1 (0.40).

Efficacy results for the primary endpoint (NPI-NH psychosis score after 6 weeks of treatment [Day 43] demonstrated a significant (p=0.0451; effect size [Cohen's d]= -0.320) treatment effect for pimavanserin compared with placebo. Prespecified subgroup analyses supported a clinically relevant treatment effect in the pimavanserin group, as a larger effect size was generally observed in subjects with more severe psychosis. Similarly, the proportion of responders (subjects with 30% and 50% reductions from Baseline) was statistically significantly greater in the pimavanserin group compared to placebo (Table 1–2). On the endpoint of mean change in NPI-NH psychosis score at Week 12, pimavanserin achieved improvement to Week 12 but the difference from placebo was not maintained due to an observed improvement in the mean score in the placebo group between Weeks 6 and 12.

Table 1–2 NPI-NH Psychosis Score Percent Responder Analysis – Full Analysis Set – Week 6 (Day 43)

| | Percent Improvement from Baseline | | | | |
|--------------------------------------|-----------------------------------|--------|--------|--------|--------|

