4.4 Subject Withdrawal or Termination

In accordance with the Declaration of Helsinki and other applicable regulations, a subject has the right to withdraw from the study at any time, and for any reason, without prejudice to his or her future medical care.

If consent has been given by a legally acceptable representative (LAR) because the subject is not competent to provide informed consent, the LAR has the right to withdraw the subject from the study at any time, and for any reason, without prejudice to the subject's future medical care or any penalty or loss of benefits to the LAR.

Subjects may be discontinued or withdrawn from the study for a number of reasons, including, but not limited to, those listed below:

- Adverse event
- Death
- Lack of efficacy
- Lost to follow-up
- Non-compliance with study drug
- Use of prohibited medication
- Physician decision
- Pregnancy
- Protocol deviation
- Study terminated by Sponsor
- Subject or LAR withdraws consent
- Other

If at any time the C-SSRS or GCAS results for a given subject reveal potential suicidality, then the Investigator should assess the clinical significance of such results. If a clinically

significant risk of suicidality is identified for a subject, then the Investigator should discontinue the subject and implement appropriate treatment (Sections 6.3.5 and 6.3.6).

Every reasonable effort should be made to complete Visit 7/ET and the safety follow-up period if a subject discontinues from the study for any reason.

If a subject is lost to follow-up, every reasonable effort should be made to phone the subject approximately 4 weeks after last known contact with the subject in order to assess the subject's current status. All phone contact with the subject should be documented.

For subjects who continue to be followed for safety, SAEs should continue to be reported as described in Section 7.4.2.

If a subject is discontinued from the study because of an AE, every reasonable attempt should be made to follow the subject until the AE resolves or until the Investigator deems the AE to be chronic or stable.

All SAEs will continue to be followed until such events have resolved or the Investigator deems them to be chronic or stable.

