8 CLINICAL MONITORING

Routine monitoring of study sites is described in Section 11.

Clinical site monitoring is conducted to ensure that the rights and well-being of human subjects are protected, that the reported study data are accurate, complete, and verifiable, and that the conduct of the study is in compliance with the currently approved protocol and amendment(s) as applicable, with GCP, and with applicable regulatory requirements. Details of the study site monitoring process are described in a separate clinical monitoring plan document.

STATISTICAL METHODS AND DATA ANALYSIS

9.1 **Statistical and Analytical Plans**

Statistical methods will be documented in detail in a statistical analysis plan to be approved by the Sponsor prior to database lock.

9.2 **Statistical Hypotheses**

No formal testing of efficacy or safety hypotheses is planned. Safety and efficacy outcomes will be summarized descriptively.

9.3 **Sample Size Determination**

Approximately 1500 subjects will be screened to enroll approximately 750 subjects, allowing for a 50% screen failure rate. Approximately 375 subjects will be randomized to the pimavanserin group as well as the placebo group (i.e., 375 subjects in each treatment group). With an assumed dropout rate of 30% in the double-blind phase, 525 subjects in total are expected to complete the study.

A sample size of 375 subjects in each treatment group ensures that within each treatment group, the probability of observing at least 1 AE with a true incidence of 1.0% is 0.977; the probability of observing at least 1 AE with a true incidence of 1.5% is 0.997; and the probability of observing at least 1 AE with a true incidence of 2.0% is 0.999.

9.4 **Subject Populations for Analysis**

The primary analyses will be based on the Safety Analysis Set. The Safety Analysis Set is defined as all subjects who take at least one dose of study drug.

The Full Analysis Set (FAS) includes all randomized subjects who received at least one dose of study drug and have both a Baseline CGI-S and at least one post-Baseline value for the CGI-I or CGI-S. The FAS will be used for the analysis of all efficacy endpoints.

9.5 **Description of Statistical Methods**

9.5.1 **Primary Analyses**

Safety results will be summarized by treatment group using descriptive statistics. Adverse events will be classified into standard terminology using MedDRA. All AEs will be listed and TEAEs will be summarized by system organ class and preferred term.

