4 ANALYSIS SETS

4.1 Randomized Analysis Set

The Randomized Analysis Set will include all subjects who were randomized. Subjects will be classified according to their randomized treatment assignment.

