4.3 Full Analysis Set

The Full Analysis Set will include all subjects in the Randomized Analysis Set who received at least one dose of study drug and have both a Baseline CGI-S and at least one post-Baseline value for either the CGI-I or CGI-S. Subjects will be classified according to the randomized treatment assignment.

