5.1 General Data Reporting Conventions

For continuous variables, the following summary statistics will be provided: number of subjects, mean, standard error of the mean (SE), standard deviation (SD), minimum, maximum, and median. Unless specified otherwise, means, medians, and confidence intervals (CIs) will be presented to one more decimal place than the raw data, and the

standard deviations and standard errors will be presented to 2 more decimal places than the raw data. .

Unless specified otherwise, all statistical tests will be 2-sided hypothesis tests performed at the nominal significance level of 5% for main effects and all confidence intervals (CIs) will be 2-sided 95% CIs. P-values will generally be presented to 4 decimal places; values less than 0.0001 will be presented as <0.0001.

For categorical variables, summaries will include the number and percentage of subjects in each category, using the number of subjects with non-missing values as the denominator for the percentages (unless otherwise specified). Categories with zero counts will not have zero percentages displayed. Percentages will be presented to 1 decimal place.

When converting number of days to months, it will be calculated as the number of days divided by 365.25 and then multiplied by 12. When converting number of days to years, it will be calculated as the number of days divided by 365.25.

All safety endpoints will be summarized using the Safety Analysis Set. The Full Analysis Set will be used for summaries of all efficacy endpoints.

Descriptive summaries of all safety and efficacy endpoints will be provided.

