12 EFFICACY ANALYSES

All efficacy analyses will be performed using the Full Analysis Set and the planned treatment assignments based on the randomization schedule. Descriptive summaries of all efficacy endpoints will be provided.

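### The CGI-I analysis that counts missing as non-response is run in the FAS, so treated subjects with no post-Baseline CGI are never imputed

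*SAP*

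**What the plan says.** SAP 13.4.2.2 defines a CGI-I responder as a score of 1 or 2 and plans two analyses at each post-Baseline timepoint. One uses observed cases. The other has "Missing values imputed as non-responders for the given visit". Both lead to a difference in percent responders with weights stratified by region, a p-value and a 95% CI. The section names no analysis population.

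The population comes from elsewhere:
- SAP 12: "All efficacy analyses will be performed using the Full Analysis Set and the planned treatment assignments based on the randomization schedule".
- SAP 5.1: "The Full Analysis Set will be used for summaries of all efficacy endpoints".
- Protocol 9.4: "The FAS will be used for the analysis of all efficacy endpoints".
- SAP 4.3 admits to the FAS only randomised subjects who took a dose and "have both a Baseline CGI-S and at least one post-Baseline value for either the CGI-I or CGI-S".

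A wider set exists: "The Randomized Analysis Set will include all subjects who were randomized" (SAP 4.1). No efficacy analysis is assigned to it.

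**The concern.** The two responder analyses differ only in how they treat a missing rating. The imputed version brings subjects without a rating into the denominator. Yet its population has already removed the subjects whose post-Baseline CGI ratings are all missing. They appear in neither numerator nor denominator.

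The exclusion has no technical purpose here. A repeated-measures model needs at least one post-Baseline value; a binary endpoint with missing set to non-response does not. Baseline CGI-S is not used in this comparison either, because stratification is by region alone.

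Membership of the FAS is decided after randomisation and could be affected by treatment, for example through early intolerance with no ET visit. So the imputed analysis does not preserve the comparison of all randomised, treated subjects. SAP 1 says that formal comparisons were added for selected efficacy endpoints to support potential regulatory submissions, and SAP 13.4.2.2 attaches a p-value and CI to this difference.

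**Working it through.** **The plan's own figures.** SAP 3.5 gives no figure for the responder analysis. What it does give reproduces: 1 − (1 − p)^375 is 0.977, 0.997 and 0.999 for p = 1.0%, 1.5% and 2.0%, and 750 × 0.70 = 525 completers.

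**Does any other section close the gap?** No. The observed-case version removes more subjects. The analysis without affected Ukraine data (SAP 3.7) also only removes subjects. SAP 6 counts and lists those outside each analysis set, but does not change the estimate.

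**Effect on the estimate.** Let r1 and r0 be the responder proportions in the FAS (pimavanserin, placebo), and e1 and e0 the shares of treated subjects with no post-Baseline CGI. Adding those subjects back as non-responders gives

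difference = r1(1 − e1) − r0(1 − e0).

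The documents give none of these four quantities. Assume r1 = 0.40 and r0 = 0.30, and vary the loss between 2% and 5%:

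| Loss, pimavanserin v placebo | Calculation | Difference (FAS: 10.0 points) |
|---|---|---|
| 3% v 3% | 0.40 × 0.97 − 0.30 × 0.97 = 0.388 − 0.291 | 9.7 |
| 5% v 2% | 0.40 × 0.95 − 0.30 × 0.98 = 0.380 − 0.294 | 8.6 |
| 2% v 5% | 0.40 × 0.98 − 0.30 × 0.95 = 0.392 − 0.285 | 10.7 |

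Each arm's percentage falls by r × e. The difference falls when r1e1 exceeds r0e0 and rises when it is smaller. With these rates it rises only if placebo loss is more than 0.40/0.30 = 1.33 times pimavanserin loss.

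**In whole subjects.** Assume 375 treated per arm and about 40% v 33% response in the FAS. P-values are from an unstratified Pearson chi-square, as an approximation to the stratified analysis.

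| Excluded | FAS | All treated |
|---|---|---|
| 11 v 11 (3% each) | 146/364 v 120/364: 7.1 points, p = 0.045 | 146/375 v 120/375: 6.9 points, p = 0.047 |
| 19 v 8 (5% v 2%) | 142/356 v 121/367: 6.9 points, p = 0.053 | 142/375 v 121/375: 5.6 points, p = 0.108 |
| 8 v 19 (2% v 5%) | 147/367 v 117/356: 7.2 points, p = 0.045 | 147/375 v 117/375: 8.0 points, p = 0.022 |

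**Scale in an earlier study.** Protocol 1.3.2 reports that study ACP-103-019 randomised 90 and 91 subjects, with "178 subjects included in the Full Analysis Set (FAS; n=87 pimavanserin and n=91 placebo". All three subjects outside the FAS were on pimavanserin. Its responder table (Table 1–2) also set missing values to non-response and fits denominators of 87 and 91. Adding the three back as non-responders:
- at least 50% improvement: 44/87 v 31/91 = 50.6% v 34.1%, 16.5 points, p = 0.026; with 44/90 = 48.9%, 14.8 points, p = 0.043;
- at least 30% improvement: 48/87 v 34/91, 17.8 points, p = 0.017; with 48/90, 16.0 points, p = 0.031.

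These are unadjusted chi-square p-values. The published ones (0.0240 and 0.0159) use a method that is not stated. The pimavanserin safety percentages fit a denominator of 90 (16.7% = 15/90, 8.9% = 8/90, 23.3% = 21/90), so the three appear to have been treated.

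**The case against.** The strongest case against giving this much weight is that few subjects can be affected and that the direction is unknown.

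- *The group should be small.* CGI-S and CGI-I are rated from Week 1 and at ET, and CGI-S also at unscheduled visits. Protocol 4.4 adds: "Every reasonable effort should be made to complete Visit 7/ET and the safety follow-up". SAP 5.3.1 lets ET and unscheduled data count. One rating of either scale keeps a subject in the FAS and open to imputation at other visits. This stands. It shrinks the gap without closing it, since reasonable effort does not guarantee a visit.
- *The Baseline CGI-S condition excludes almost nobody*, because inclusion criterion 7 requires a qualifying score at Visit 2. This stands.
- *The endpoint is exploratory* (SAP 12.1), without multiplicity adjustment (SAP 12.4), and the version log calls the added p-values nominal. This stands and limits the stakes.
- *Early intolerance is still reported.* TEAEs, including those leading to discontinuation, are analysed in the Safety Analysis Set, and SAP 6 lists exclusions with reasons. True, but the responder estimate itself stays uncorrected.

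A reader might go further and infer that the rule hides the earliest treatment failures and favours pimavanserin. The documents do not support that. Some early exits have causes that precede treatment, such as a central read of the Baseline ECG outside the allowed range (protocol 6.3.4). Study ACP-103-019 does not settle the direction: its FAS rule and the reasons for its three exclusions are not given, and the same section reports fewer discontinuations for TEAEs on pimavanserin (8.9%) than on placebo (12.1%), over the whole study and not only early. Nor does SAP 13.4.2.2 state a purpose for the imputed version; that it is meant to guard against dropout is an inference.

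**Conclusion.** The gap is real and follows directly from SAP 4.3, 12 and 13.4.2.2: treated subjects with no post-Baseline CGI are never imputed. Responder percentages are overstated in any arm that has such subjects. Equal loss barely matters (10.0 to 9.7 points at 3% in each arm). Loss that differs by three percentage points moves the difference by roughly 0.7 to 1.4 points, down or up according to which arm loses more. These sizes rest on assumed response rates of 30% to 40% and assumed loss of 2% to 5%. Study ACP-103-019 shows scale only. Given a small affected group and an exploratory endpoint with nominal p-values, this is a cheap improvement to the plan. It does not threaten the trial's primary safety conclusions.

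**What to change.** In SAP 13.4.2.2, run the missing-as-non-responder version in all randomised subjects who took at least one dose, classified by randomised arm, with no post-Baseline CGI requirement. This is not quite the Safety Analysis Set, which classifies by treatment actually received. Keep the FAS for the observed-case version. State the exception in SAP 5.1 and SAP 12, and list it in SAP 19 as a change from protocol 9.4. Beside the result, give the number in each arm outside the FAS with reasons; SAP 6 already plans the counts and the listing.

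Cost: a few sentences and a different denominator, with no new data. Responder percentages will be slightly lower, and there is one more denominator to explain.

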13.4.3 SDI

Observed SDI scores will be summarized using descriptive statistics at Baseline, Week 4, and Week 8/ET. The change from Baseline values will be summarized descriptively at Week 4 and Week 8/ET. The change from Baseline in SDI score will also be analyzed using the MMRM model as described in Section 13.2.

13.4.4 EQ-5D-5L

13.4.4.1 **VAS ANCOVA**

The change from Baseline in the EQ-5D-5L VAS score will be summarized using an ANCOVA model with effects for region, treatment group, and Baseline score.

Observed EQ-5D-5L VAS scores will be summarized using descriptive statistics at Baseline and Week 8/ET. The change from Baseline values will be summarized descriptively at Week 8/ET. The change from Baseline in EQ-5D-5L VAS score will also be analyzed using OC and ANCOVA LOCF as specified in Section 13.3.

